3.11.2 IA-2 (or IA- 1^n)

- 1. Test primary and secondary efficacy hypotheses in the pre-specified hierarchy. If efficacy boundaries for the primary and the first two secondary endpoints are crossed then the trial may be stopped early and the final analysis is planned with the overruns
- 2. If the efficacy boundaries for the primary endpoint and the first two secondary endpoints (i.e. for sensitivities and specificities for detecting impaired safety with Thin-BA, Mild-BA and Moderate-BA) are not crossed then consider sample size re-estimation (SSR) using the promising zone approach (Mehta and Pocock, 2011, Statistics in Medicine).
 - Calculate conditional power (CP) for sensitivities and specificities for the primary efficacy (Thin-safety). If $0.5 \leq CP \leq 0.9$ then increase sample size to meet CP = 0.9 up to a maximum of 1300 subjects overall (including the IA-1 subjects)
 - If CP < 0.5 or CP > 0.9 then the trial continues as planned.
 - If CP < 0.2 then consider futility

3.11.3 Interim Safety Analysis

Although the DDS device has been deemed Non-Significant Risk by the CDRH, FDA, the iDMC will be decide on the safety of the device and the trial based on the adverse events data presented at the interim analysis meeting by the independent statistical center. The iDMC may recommend stopping the trial if they have safety concerns about the device or the trial.

3.11.4 Interim Monitoring

Prevalence of impaired swallow safety and efficiency using different consistency swallows is a key parameter in powering of this trial. The assumed prevalence during the designphase is between 30% - 40%. Observed prevalence may in fact be out of this range and can have serious impact on the power of the trial. For this reason, prevalence of impaired swallow safety and efficiency will be monitored in a blinded fashion throughout the trial. Furthermore, due to technical problems, it is foreseen that a small percentage of videos may not be readable by the core lab readers. Again this would be monitored in a blinded fashion. For the purpose of blinded monitoring, only the data from the central VFSS laboratory, site identification and patient medical condition will be used.

3.12 Reporting

3.12.1 Patient Disposition

The number and percentage of patients will be tabulated for each of the following categories by disease group:

- Screened (total only);
- Full Analysis Set (mITT population); overall and by disease group
- PPS population; overall and by disease group
- Safety population;
- Patients who complete the study;
- Patients who has early termination of protocol and reason for early termination
- Patients who were successfully screened and enrolled but did not start the study protocol (excluded from the FAS).
- Protocol deviations will be summarized by deviation type

3.12.2 Baseline Demographics

Baseline demographics will be presented for the overall population as well as stratified by disease group and by site. Summary measures will include percentage for categorical variables and lower 25%, median, upper 75%, mean and standard deviation for continuous variables.

Along with the demographic data, the following disease characteristics will be summarized for the FAS:

- Inpatient (Acute vs. inpatient rehabilitation)/Outpatient split
- Inpatient primary admission diagnosis
- Inpatient secondary admission diagnosis
- Invasive mechanically ventilated patients
- Outpatient reason for referral for VFSS
- Outpatient previous diagnoses
- NIH Stroke scale (stroke subjects only)

Baseline and all above patient characteristics will be presented for the FAS overall population as well as stratified by primary daignosis group (Stroke, Other Neuro and Other).

3.12.3 Study Administration

For each consistency and swallow count the number of subjects completing that particular swallow will be reported. This will be stratified by consistency and disease group (also overall).

3.12.4 Efficacy Analysis

For each of impaired safety and efficiecy, point estimates and confidence interval will be presented for sensitivities and specificities by bolus consistencies. This will be presented for the overall FAS. P-value for testing the efficacy hypothesis in Equation (1) will be reported for the primary efficacy endpoint. In addition, if the primary efficacy hypothesis test meets statistical significance then p-values for secondary efficacy analysis will also be presented in a hierarchical fashion until the first non-significance level for efficacy analysis at each interim and final analysis will be obtained using the LDOF spending function [2].

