14.8 Datasets to be analyzed

14.8.1 Full analysis dataset

For this trial, ITT population is defined as the population able to complete at least 1 THIN-Ba bolus. Missing data will be reported and sensitivity analysis carried out. The analysis of primary and secondary endpoints will be performed to evaluate DDS performance and will be carried out using data from this population. The THIN-Ba consistency boluses (up to 4) with available simultaneous VFSS and DDS data per patient will be included into the analysis. As will the MILD-Ba and MOD-Ba consistency boluses (up to 3 each) with simulultaneous VFSS and DDS data per patient.

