3.1 Success Criteria and Hypothesis Testing

The success criteria for the DDS device validation trial is that the sensitivity is greater than 80% with a specificity greater than 50%. The sensitivity and the specificity will be estimated using an independent validation dataset. The following one-sided hypothesis testing will be carried out:

$$H_0 : H_0^{se} \cup H_0^{sp} \text{ vs.}$$

$$H_A : H_A^{se} \cap H_A^{sp},$$
(1)

where,

 $\begin{array}{lll} H_0^{se} & : & \mathrm{Sensitivity} \leq .8, \\ H_A^{se} & : & \mathrm{Sensitivity} > .8, \\ H_0^{sp} & : & \mathrm{Specificity} \leq .5, \text{ and} \\ H_A^{sp} & : & \mathrm{Specificity} > .5. \end{array}$

Each of H_0^{se} vs. H_A^{se} and H_0^{sp} vs. H_A^{sp} will be tested at one-sided 2.5% level of significance which will (conservatively) preserve the over-all type-I error for testing H_0 vs. H_A .

The same hypothesis test as in (1) will be applied to the secondary endpoints. Hypothesis will be carried out in a hierarchical fashion to ensure that the type-I error is controlled at the one-sided 2.5% level.

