3.3 Group Sequential Design (GSD)

The clinical trial will initially start as a 3-look GSD. Alpha-spending will be calculated using Lan-DeMets spending function with O'Brien-Fleming parameter (LDOF) [2]. At the first interim analysis (IA-1) the threshold on the ROC curve may be re-computed using the ROC curve generated using the IA-1 data, in which case, the validation trial would start afresh following IA-1 using a 2-look GSD. Data included in the IA-1 would no longer be used for the validation phase. If the threshold is not re-computed at the first interim and the efficacy boundary has not been crossed then the trial continues as planned as a 3-look GSD.

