3.5 Group Sequential Design and Sample Size Re-estimation Details

Due to uncertainties about the population parameters and their influence on the power, an adaptive sample size re-estimation (SSR) is proposed. This is after the first interim the trial continues as a 3-look GSD with out changing the threshold then a SSR would be done at the second interim analysis while if the threshold is changed at the first interim then the SSR will be carried out at the only interim analysis time for the freshly started validation trial post threshold re-calibration. The following adaptation rules will be applied:

- 1. If the threshold is changed based on the first interim look, then a new appropriately powered (80%-90%) 2-look group sequential design trial will be started. The powering will be based on the sensitivity and specificity estimates obtained at the first interim. The interim and the final analysis for this new trial would not include the data from subjects included in the first interim analysis.
- 2. At the interim of the new validation trial, unless the interim Z statistic crossed the efficacy boundary, a sample size re-estimation based on conditional power being in the promising zone [1] will be carried out. Conditional power (CP) will be calculated both for sensitivity as well as specificity. Promising zone is defined as both the CPs are between 50% and 90%. Futility may also be decided in case of low conditional power for either sensitivity or specificity.
- 3. The increase will be determined equating CP to the desired power of 90%. This will be bracketed by a minimum increase of 50 subjects and max increase defined by the maximum sample size of 1300.
- 4. In case the threshold is not changed at the first interim, the trial continues as a 3-look GSD and the SSR adaptation rules in 2-3 above will apply at the second interim look.

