3.9 Analysis Sets

3.9.1 Full Analysis Set (FAS)

The FAS is based on a modified-intent-to-treat ppulation which is defines as all subjects with a signed informed consent and at least one analyzable swallow with the Thin-BA boluses using the VFSS.

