3.11.1 Interim Analysis - 1 (IA-1)

The main objective of IA-1 is to determine if the fixed threshold (fixed using phase-0 data) applied to the ROC curve obtained using IA-1 data is still optimal or whether a new threshold obtained from the IA-1 data should be used moving forward. In case the threshold is changed then the validation trial re-starts while excluding the IA-1 data for testing validation related hypotheses.

The Analysis plan for IA-1 are listed as follows:

- 1. Compute AUC for the ROC curve based on IA-1 data
- 2. If AUC < .75, consider futility analysis. Note that this futility rule is non-binding.
- 3. Otherwise, calculate sensitivity, specificity both with the fixed threshold from phase-0 data as well as the optimal threshold on the IA-1 ROC curve.
- 4. The benefit versus the cost of changing the threshold will be analyzed. This will be done by comparing the conditional power at IA-1 under the old threshold and a total sample size of N = 900 ($CP_{old,900}$) with the power of a restarted trial using the new threshold and sensitivity-specificity estimates obtained at IA-1 using this new threshold along with the prevalence estimate obtained at IA-1. If the power of the restarted trial with $N = 900 - N_1$ is greater than $CP_{old,900}$ then the benefit of changing the threshold is clear. Here N₁ is the number of subjects included in the IA-1 analysis. If this is not the case then the power of the restarted trial with N = 900 ($P_{new,900}$) will be compared to $CP_{old,900}$. Since conditional power and power will be calculated for testing both sensitivity and specificity for the primary endpoint the formal guideline (established using simulations) is defined in terms of the product of the two as follows:

If $P_{new,900-N_1,SE} \times P_{new,900-N_1,SP} > CP_{old,900,SE} \times CP_{old,900,SP}$ then change threshold; OR

If $P_{new,900,SE} \times P_{new,900,SP} > CP_{old,900,SE} \times CP_{old,900,SP} + 0.025$ then change threshold.

The above statistical logic offers a guideline for changing the threshold, however clinical justification may overrule the statistical guideline in this matter.

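### After a threshold change at the first interim analysis, the SAP gives two conflicting populations for the reported sensitivity and specificity

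*SAP*

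**What the plan says.** **Rules that keep the IA-1 subjects.** SAP 3.12.4 covers the efficacy tables. It asks for point estimates and confidence intervals for sensitivity and specificity by consistency, and adds "This will be presented for the overall FAS". SAP 3.9.1 defines the FAS as "all subjects with a signed informed consent and at least one analyzable swallow with the Thin-BA boluses using the VFSS". Protocol 14.8.1 defines an ITT population by completion of at least one thin-barium bolus and says that the primary and secondary analysis "will be carried out using data from this population". Neither definition removes IA-1 subjects under any condition.

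**Rules that remove them after a threshold change.** SAP 3.1: "The sensitivity and the specificity will be estimated using an independent validation dataset". SAP 3.5, item 1: "The interim and the final analysis for this new trial would not include the data from subjects included in the first interim analysis". SAP 3.3: "Data included in the IA-1 would no longer be used for the validation phase". SAP 3.11.1 speaks of "excluding the IA-1 data for testing validation related hypotheses". SAP 2.3 and Protocol 9, 14.3 and 14.5 agree.

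**What links the two.** Nothing does. SAP 3.9 lists a full analysis set, a per-protocol set derived from it, and a safety set. The test statistics in SAP 3.7 use the numbers of diseased and healthy subjects in an analysis dataset that is tied to none of these.

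**The concern.** A threshold picked as optimal on the IA-1 data looks better in those data than in new patients. That is why the design discards IA-1 after a revision. If the tables are programmed from 3.12.4 and 3.9.1 as worded, the calibration subjects return to the headline accuracy. The estimate would be somewhat optimistic and its interval would claim more independent information than exists. Neither need agree with a test run on the validation subjects alone.

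This is a pivotal device validation, so the reported estimate and interval are what users will quote. The branch is not rare: in SAP Table 5-2 the threshold changes in 0.33 to 0.74 of runs, depending on the row (0.33 to 0.36 at 90% sensitivity and 60% specificity).

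**Working it through.** **1. How many calibration subjects are involved.** SAP 3.4 times IA-1 by a 95% interval for prevalence no wider than 15%. With n = (2 × 1.96 × √(p(1−p)) / 0.15)²:
- p = 0.20: n = 109.3 (the SAP says 110)
- p = 0.35: n = 155.4
- p = 0.50: n = 170.7 (the SAP says around 170)

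The SAP's figures reproduce. With checks every 50 subjects, 35% prevalence gives 200, as the SAP says. SAP 3.2 allows 100 to 200 calibration subjects, a starting total of 900 and a maximum of 1300. They would therefore make up between 100/1300 = 8% and 200/900 = 22% of the FAS.

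**2. Interval width.** Inputs are the SAP 3.2 planning values: sensitivity 86%, specificity 60%, prevalence 35%. The SAP names no interval method, so Wald 95% half-widths are used: 1.96 × √(p(1−p)/n), with n = 0.35N for sensitivity and 0.65N for specificity.

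| Set | N | Sensitivity, ± points | Specificity, ± points |
|---|---|---|---|
| Without IA-1 | 700 | 4.3 | 4.5 |
| Overall FAS | 900 | 3.8 | 4.0 |
| Without IA-1 | 1100 | 3.5 | 3.6 |
| Overall FAS | 1300 | 3.2 | 3.3 |

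The ratios are √(700/900) = 0.88 and √(1100/1300) = 0.92, so the intervals are 12% and 8% too narrow. If 900 new subjects follow an IA-1 of 200, the ratio is √(900/1100) = 0.90, or 10%.

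**3. Optimism in the estimate.** The documents give no score distribution and do not define the optimal threshold. Assumptions: binormal scores, 35% prevalence, threshold chosen on IA-1 by the Youden index or by the product of the two powers. Pooling dilutes the in-sample optimism by the IA-1 share.
- Product of powers, with the change guideline of SAP 3.11.1, starting accuracy 86%/60%, 200 of 900: mean IA-1 sensitivity 87.7%, true 86.6%, pooled (200 × 87.7 + 700 × 86.6)/900 = 86.8%, a bias of +0.2 point.
- Same rule, starting accuracy 85%/55%: IA-1 85.2%, true 83.7%, pooled (200 × 85.2 + 700 × 83.7)/900 = 84.0%, a bias of +0.3 point.
- In-sample optimism of 4 points, towards the upper end of the settings tried: 4 × 200/900 = 0.9 point.

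Over all settings the pooled bias is about 0.2 to 1.0 point in sensitivity and 0 to 0.5 point in specificity.

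**4. Can interval and test disagree?** Take 35% prevalence and 200 IA-1 subjects out of 900: 70 impaired in IA-1 and 245 after it. Suppose the device detects 59/70 (84.3%) and 207/245 (84.5%), so that IA-1 shows no optimism at all. Pooled, this is 266/315 = 84.4%. The SAP 3.7 statistic is Z = √N_d × (estimate − 0.8)/√(0.8 × 0.2).
- Validation subjects: Z = √245 × 0.0449/0.4 = 1.76. Wald lower limit 0.8449 − 1.96 × √(0.8449 × 0.1551/245) = 79.96%.
- Overall FAS: Wald lower limit 0.8444 − 1.96 × √(0.8444 × 0.1556/315) = 80.4%. The same formula for Z gives √315 × 0.0444/0.4 = 1.97.

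The FAS interval excludes 80% while the validation test misses the nominal 1.96. A group-sequential final boundary above 1.96 would not rescue that test.

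**5. Do the exclusion rules define one set?** Not quite. SAP 2.3 starts validation with the first patient enrolled after the data cut-off; SAP 3.5 removes those included in IA-1. Protocol 12.2 counts a patient as enrolled at consent, and consent may precede the procedure by up to two weeks. Someone who consents before the cut-off and is examined after it is out under the first rule and in under the second. Thresholds are also revised separately by consistency (SAP 2.3), and no section says in terms whether one revision removes IA-1 subjects from every endpoint.

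**The case against.** The best reply is that the documents already answer the question. SAP 3.1 is the rule on estimation and names an independent dataset. SAP 3.5 item 1 covers the whole final analysis of the restarted trial, not only its tests. The word overall in 3.12.4 probably means unstratified, as it does in 3.12.1 to 3.12.3. On that reading only a cross-reference is missing.

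Much of this stands. The intent to exclude is clear. A reader might infer from 3.12.4 that the sponsor has decided to report accuracy on calibration subjects, with the p-value taken from the validation subjects. The documents do not support that. SAP 3.1 and 3.5 say otherwise, 3.12.4 assigns the p-value no set of its own, and 3.7 builds the test from the same estimates. Nor can it be inferred that the efficiency results would be biased, because SAP 2.3 describes threshold updating for swallowing safety.

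The reply does not remove the conflict. Reading overall as unstratified leaves the term FAS in place, and the FAS as defined contains the IA-1 subjects. A programmer cannot follow 3.12.4 with 3.9.1 and also 3.1 with 3.5 once a threshold has changed.

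**Conclusion.** The SAP contradicts itself on the population for reported accuracy after a threshold change, and it should be corrected. If no threshold changes, IA-1 subjects belong in the FAS and nothing is wrong.

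The size is modest. The interval narrowing of 8% to 12% rests on 200 IA-1 subjects within a total of 1300 or 900; it is smaller with fewer IA-1 subjects. The bias of 0.2 to 1.0 point in sensitivity rests on the assumed binormal scores, 35% prevalence and the threshold rules tried, and is small beside half-widths of 3 to 4 points. The more practical consequence is that a reported interval can clear 80% when the validation test does not, and this can happen without any optimism.

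**What to change.** 1. Add to SAP 3.9 a Validation Analysis Set: the FAS if no threshold is changed; otherwise the FAS minus all subjects included in IA-1, in line with 3.5 item 1.
2. State, before IA-1 is unblinded, that this one rule applies to every endpoint in the hierarchy, and reconcile the cut-off wording of 2.3 with that of 3.5.
3. Cite the set in 3.7 and 3.12.4 for estimates, intervals and p-values alike, and use it for predictive values and subgroup accuracy. Align Protocol 14.8.1.
4. Report IA-1 results in a separate table labelled as calibration data.

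This changes wording, not conduct. The cost is slightly wider intervals: in the 900-subject case, ±4.3 instead of ±3.8 points for sensitivity and ±4.5 instead of ±4.0 for specificity. Endpoints whose own threshold was not revised also lose the IA-1 subjects, which is what 3.5 item 1 already implies.

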3.12.5 Prevalence of Swallow Safety and Efficiency Impairments

Bolus level prevalence of Safety and Efficacy impairments will be summarized by swallow consistency and by swallow count. The number of missing VFSS label will also be summarized.

Subject level prevalence will also be reported similarly by swallow consistency and swallow count. Here, only the first impairment will be counted. Thus the prevalence at a particular swallow count is defined as the number of subjects showing their first impairment at that swallow count divided by the number of subjects at risk of impairment at that swallow. Cumulative prevalence will also be summarized.

Prevalence tables will also be reported stratified by primary diagnosis group and by site (in all 13 sites).

3.12.6 Safety Analysis

All safety analysis will be performed on the Safety Analysis Set. All adverse Events (AEs) will be coded using the Medical Dicotionary for Regulatory Agencies (MedDRA). A TEAE is defined as an AE that starts or worsens on or after study Day 1 (defined as the procedure day), and no more than XX days after the procedure. All TEAEs will be listed by subject number and MedDRA coding.

The number and percentage of subjects with TEAE will be summarized in several different tables:

- All TEATs by System Organ Class (SOC) and preferred term (PT)
- Study procedure related AEs by SOC and PT
- Severity of All TEAEs by SOC and PT.

A subject with 2 or more AEs within the same level of the MedDRA term will be counted only once in that level using the most extreme incident (most severe for the severity table and related for the relationship to study procedure table).

4 Blinding and Firewall for Interim Analysis

The key blinding required for this trial is the blinding of the sites to the VFSS results determined by a central VFSS laboratory and the blinding of the central VFSS laboratory to the yet-to-be validated results from the DDS available at the sites. There will be no communication between the sites and the central laboratory. The results of the VFSS on each subjects' boluses will be kept blinded and would not be available to the sites or the sponsors. It will be made available to the iDMC and the iSC members with the unblinded role through a secured firewall system immediately prior to the time of the interim and the final analyses. The details will be pre-specified in the study protocol as well as in the DMC charter.

Cytel's Access Control Execution System ACES will be used as the firewall system. This system stores all study conduct and analysis related documents in a secured and traceable way. All members of the sponsor team, iDMC, iSC and others as required are granted accounts on this system with a specified role. The roles of iDMC and iSC members carrying out the unblinded analysis at the interims will be given the "unblinded" role. All other account holders on ACES are given a "blinded" role. This is administered by the ACES administrator who also has an "unblinded" role. Members also may or may not have the rights to upload documents on the ACES system for that particular trial. Any document uploaded by a member also has a specified role "unblinded" or "blinded". The correctness of the this role assigned to the document is checked automatically as well as manually by the ACES administrator before being available according to the role to other ACES accounts. Naturally, only a user with an "unblinded" role can upload a document with an "unblinded" role.

Prior to the interim analysis iDMC meeting, all data except the VFSS data that is maintained by the database manager will be uploaded to the ACES and analysis datasets will be programmed in a blinded fashion using dummy VFSS results. Once the interim analysis is ready to be carried out, the iDMC will be required to send an notification to the central VFSS laboratory to upload the VFSS results on ACES. This document will have a "unblinded" role and will only be available to the iDMC members and the iSC members engaged in producing the interim analysis results. Once this document is uploaded in the ACES system there will be no direct communication between the sponsors and/or the sites and the "unblinded" members. All communication will then need to occur within the ACES system. The data remains blinded to the sponsors and the site until the end of the final analysis (planned or in case of an early stop).

With ACES it is possible to generate a report on all documents in the ACES system which minimally includes the following information:

- 1. Time of upload
- 2. Role specified
- 3. List of all users who have seen or had access to each particular document with the corresponding time

The general ACES methodology and process is summarized in the Figure 4-1.

References

